For the purposes of the analysis on dental-related service use and costs among Medicaid beneficiaries, all children participating in Medicaid of elementary school age will be included in the analysis, except for children in participating schools that do not provide informed consent to provide oral health and Medicaid dental service use data.

The Primary Specific Aims are to:

- 1. Determine the non-inferiority of simple vs complex caries prevention for preventing new caries (primary prevention).
- 2. Determine the non-inferiority of simple vs complex caries prevention for arresting current caries (secondary prevention).
- 3. Determine the impact of simple vs complex prevention on child oral healthrelated quality of life
- 4. Determine the impact of once per year vs twice per year care on the arrest and prevention of caries

Notably, toothaches or office based dental care reduces in-class learning time. If the caries prevention programs are as effective as predicted, knowing the time/trade-off will be important. Thus a secondary outcome of the study will be school performance (school absence and student achievement). To insure accurate assessments, program participants will be compared to children in their own schools and to children in NYC "peer schools" not participating in the study. No additional data is collected for educational outcomes from participants.

The Secondary Specific Aims are to:

- 1. Determine the impact of prevention vs no prevention on school absence
- 2. Determine the impact of prevention vs no prevention on standardized test performance
- 3. Determine the impact of simple vs complex prevention on school absence and test performance

The exclusion criteria will be those: (1) not attending participating schools, (2) those attending participating schools without informed consent, or (3) those attending participating schools with informed consent, but without assent and (4) those allergic to silver.

For the purposes of the analysis on dental-related service use and costs among Medicaid beneficiaries, the only excluded groups are (1) children not participating in Medicaid will be excluded and (2) children participating in Medicaid in Caried*Away* schools, but without informed consent to provide oral health and Medicaid dental service use data.

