3.3 Secondary Study Endpoints

School absence and academic performance data will be provided by the NYC Department of Education.

Medicaid claims, encounter, and eligibility data for elementary students in New York City enrolled in Medicaid will be provided by New York University's Wagner School of Public Service and New York University's School of Medicine.

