6.4 Control/Comparison Group and Confounding Factors

Complex prevention is the "comparison" while simple prevention is the "intervention" group. Both groups receive primary and secondary prevention and we expect both protocols to be similarly effective in reducing untreated caries.

We will include relevant confounders a priori in our analysis, including: gender, previous (or concurrent) dental treatment (identified as new or existing treated dentition at examination), age at examination, race/ethnicity, and any school-level indicators. As these data have a multilevel structure, we will additionally assess caries incidence and prevalence using multilevel mixed effects Poisson and logistic modeling (ML-MEM). We will examine the effects of comprehensive prevention at multiple levels (tooth, child, grade, and school). In this analysis, we will be able to explore the variation in clinical outcomes across child and school levels. For all GEE and multilevel models, we will conduct analysis for outcomes (caries prevalence and incidence) measured by all teeth, all adult teeth only, and all deciduous teeth only.

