7.2 Statistical Methods

For caries arrest, we will first determine the per-patient proportion of carious lesions treated with simple versus complex prevention that stayed arrested throughout the length of the study. The percentage of arrested caries (at the child level) will be modeled using multilevel binomial regression. Our noninferiority margin, δ , is set at 10%. Our null hypothesis is that simple prevention is not inferior to the complex prevention by at least δ : π_{simple} - $\pi_{\text{complex}} \ge \delta$. Our alternative hypothesis is that π_{simple} - $\pi_{\text{complex}} < \delta$. We will use differences in effect sizes as estimated by confidence intervals to determine clinical non-inferiority of the two prevention methods. For the prevention of new caries, we will use generalized estimating equations (GEE) with a logit link (caries prevalence) and a negative binomial link (caries incidence), assuming an exchangeable correlation matrix, to evaluate longitudinal effects of comprehensive care untreated decay. We will identify the number of teeth at risk for each child during each follow-up interval and determine the number of those teeth in which new caries is observed at the examination that ends that interval. Primary teeth lost in each interval and new permanent teeth will not contribute to data for that interval. To explore non-linear trends in untreated decay between simple and complex prevention, we will use generalized additive models (GAMs) with non-parametric smoothers. Longitudinal effects of simple and complex prevention on academic outcomes, compared to untreated children, will be analyzed using propensity score-matching and multilevel modeling. First, we will estimate propensity scores for each participant at baseline, establishing the probability of treatment assignment conditional on observed covariates (e.g., prior academic performance). Propensity scores will be used to match treatment students to students not receiving treatment, considering multiple forms of matching
such as nearest neighbor and caliper. Treated students and matched comparators will then be analyzed using multilevel mixed effects linear regression (for academic achievement) and Poisson regression (for school absences).

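### The academic outcome models specify no baseline score or absence term, and no model is written for the randomised simple vs complex academic comparison

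*Combined protocol and SAP*

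**What the plan says.** Section 1.2 lists three secondary academic aims. Aims 1 and 2 compare prevention with no prevention, on absence and on test performance. Aim 3 compares the two programmes: "Determine the impact of simple vs complex prevention on school absence and test performance". Section 3.3 gives the source: "School absence and academic performance data will be provided by the NYC Department of Education".

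The academic paragraph of section 7.2 is framed as "Longitudinal effects of simple and complex prevention on academic outcomes, compared to untreated children". A propensity score is estimated for each participant at baseline, "establishing the probability of treatment assignment conditional on observed covariates (e.g., prior academic performance" being how its content is described. Its use is then stated: "Propensity scores will be used to match treatment students to students not receiving treatment". The outcome step follows: "Treated students and matched comparators will then be analyzed using multilevel mixed effects linear regression (for academic achievement) and Poisson regression (for school absences". No covariates are listed for either outcome model.

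Section 6.4 has a general adjustment statement: "We will include relevant confounders a priori in our analysis, including: gender, previous (or concurrent) dental treatment", followed by "age at examination, race/ethnicity, and any school-level indicators". Prior scores and prior absences are not named there, and the section goes on to describe caries models.

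**The concern.** A student's earlier score and earlier absence count are natural candidates for the strongest predictors of the later ones. The plan presumes that prior performance is available, yet assigns it only to matching. This matters differently for the two kinds of comparison.

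- **Aim 3 (randomised).** Matching treated to untreated children does not adjust the contrast between simple and complex schools. No other academic analysis of that contrast is written, so a main source of precision is left unspecified.
- **Aims 1 and 2 (not randomised).** Participation depends on parental consent. Matching on a single score can leave differences in prior achievement between matched groups, and prior absence is not named even as a matching variable.

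The plan treats other outcomes differently. The caries prevention power calculation in section 7.1 controls for baseline untreated decay. The Medicaid analysis in section 7.2 uses difference-in-differences, so the earlier level of the outcome enters the effect estimate. Only the academic outcomes have no stated baseline term. Two analysts could fit different models and both claim to have followed the plan.

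**Working it through.** **1. The plan's own figures.** Section 7.1 powers caries arrest and caries prevention only. The arrest figure reproduces. With 20% in both arms, margin 10%, one-sided 5% and 80% power, n = (1.645 + 0.842)² × 2 × 0.20 × 0.80 / 0.10² = 198 per group, 396 in total. The design effect is 1 + (235 − 1) × 0.10 = 24.4, and 396 × 24.4 = 9,662. None of this concerns an academic endpoint. The documents give no academic effect size, SD, ICC, power or baseline-outcome correlation. The repeated measures correlation of 0.5 in section 7.1 is for caries.

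**2. Assumptions needed.** Two-sided 5% test; 80% power without adjustment; ICC 0.10, borrowed from caries arrest; 30 vs 30 schools (section 3.1); m = 235 students per school (section 7.1) or an assumed 100. Baseline-outcome correlations are assumed: rb between schools, rw within schools.

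**3. Formula.** For the difference in means between arms, in SD units:

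variance = (2/30) × [ICC × (1 − rb²) + (1 − ICC) × (1 − rw²)/m]

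Let k be the adjusted variance divided by the unadjusted variance (rb = rw = 0). Adjusted power = Φ(2.802/√k − 1.960), where 2.802 = 1.960 + 0.842.

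**4. Same correlation at both levels.** Then k = 1 − r², whatever the ICC or m.

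| r | k | 2.802/√k | Adjusted power |
|---|---|---|---|
| 0.2 | 0.96 | 2.859 | 81.6% |
| 0.3 | 0.91 | 2.937 | 83.6% |
| 0.5 | 0.75 | 3.235 | 89.9% |
| 0.7 | 0.51 | 3.923 | 97.5% |
| 0.8 | 0.36 | 4.669 | 99.7% |

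**5. Baseline explains only within-school variance (rb = 0).**

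- m = 235, rw = 0.5: unadjusted bracket 0.10 + 0.90/235 = 0.10383; adjusted 0.10 + 0.90 × 0.75/235 = 0.10287; k = 0.991; power 80.4%.
- m = 100, rw = 0.5: 0.10900 becomes 0.10675; k = 0.979; power 80.8%.
- rw = 0.8: 80.9% at m = 235 (k = 0.976) and 82.1% at m = 100 (k = 0.10324/0.10900 = 0.947).

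At m = 235 the between-school part is 0.10/0.10383 = 96% of the variance, so a covariate that acts only within schools can do little.

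**6. Baseline explains only between-school variance (rw = 0, rb = 0.5, m = 235).** The adjusted bracket is 0.10 × 0.75 + 0.90/235 = 0.07883; k = 0.759; power 89.5%. Almost all the gain in step 4 therefore comes from the school level, which is why the school mean of the baseline belongs in the model.

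**7. Limits.** These figures are for a continuous outcome in the randomised contrast. Nothing has been computed for the Poisson absence model, or for residual confounding in Aims 1 and 2.

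**The case against.** The strongest reply is that silence is not exclusion. Section 7.2 gives no covariate list for the academic models, and its one mention of prior performance is offered as an example. Section 6.4 promises relevant confounders, in an open-ended list that includes school-level indicators; these could cover prior achievement. The analysis is called longitudinal, so a repeated-measures model might carry the baseline score. This stands: a reader might infer that the models leave the baseline out, or that the simple vs complex comparison gets no adjustment of any kind, and the documents support neither. They support only that no such term is specified. Whether section 6.4 reaches the academic outcomes is unclear.

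A reader might also attach one figure to the loss, for example about 9 or 10 points. That needs both 80% starting power and a correlation near 0.5 at both levels, and the documents give neither for academic outcomes.

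Nor should the Aim 3 comparison be called biased: randomisation of schools protects it from systematic baseline differences. For Aims 1 and 2, matching on prior performance, with calipers under consideration, already addresses part of the confounding. What remains is not quantified here.

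Finally, prior data may be incomplete. Children are eligible from PK (section 3.1), new students may join each year (section 6.1.1), and section 3.3 does not say which school years the Department of Education data cover. This limits the fix but does not remove the reason for it.

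**Conclusion.** The point holds as a gap in specification with a practical cost. Prior academic performance is named only as an example matching covariate, prior absence is not named at all, the outcome models state no baseline term, and Aim 3 has no written academic model.

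From 80% unadjusted power, the gain from adjustment runs from about 0 to 20 points. It is under 1 point when the baseline explains only within-school variance (rw = 0.5, ICC 0.10, 100 to 235 students per school), and about 4, 10 and 17.5 points when the correlation is 0.3, 0.5 and 0.7 at both levels. The between-school correlation decides where in that range the trial falls, and the documents do not give it. For Aim 3 the loss is precision. For Aims 1 and 2, adjustment would also reduce residual confounding.

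These are secondary endpoints on which the trial was not powered, and the primary caries conclusions are unaffected. The change is still worth making because it costs so little.

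**What to change.** In section 7.2:

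1. Write the simple vs complex academic model (Secondary Aim 3) explicitly, as a comparison of the randomised schools, separate from the matched analysis.
2. In all academic outcome models, include the student's own prior test score (achievement) or prior absence count (absences), plus the school mean of that value.
3. Define the prior value as that of the last school year before the school's programme start, with the same calendar period for comparators. A definition tied to enrolment would not work for comparators, who never enrol.
4. Add prior absence to the propensity model.
5. State how missing prior values are handled. In the randomised comparison, a missing-baseline indicator is adequate. In the participant vs non-participant comparisons such an indicator can itself leave bias, so use multiple imputation or match on missingness.

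The cost is SAP wording, a few extra covariates, and confirmation that the Department of Education data cover the pre-programme year. Some young children will have no prior test score, and the missing-data rule is there for them. No clinical procedure changes.

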7.3 Subject Population for Analysis

For study outcomes, participants will be analyzed using intent to treat. All participants will be analyzed as randomized in the original randomization, regardless of whether or not they received an intervention.

For dental-related service use and costs, all New York City elementary school-age children enrolled in Medicaid will be analyzed using intent-to-treat.

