2.1 Primary Objective

To determine if simple prevention is non-inferior to complex prevention for caries arrest and longitudinal caries prevention.

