The inclusion criteria for the schools enrolled in groups (1) and (2) include: A Hispanic/Latino population of at least 50% and a free and reduced lunch population of at least 80%. The remaining racial/ethnic and socioeconomic of the schools beyond these criteria can include children from any race/ethnicity and economic background. The inclusion criteria for schools in group (3) include any elementary school in New York City. Schools in group (3) will be balanced to ensure representation from every primary race/ethnic group and from all socioeconomic tertiles.

The impact of COVID-19 has greatly impacted our in school-based cavity prevention approach. Elementary schools have closed, delayed in opening and will either allow students to return to schools part-time under a blended learning model or will learn at home remotely full-time. This has impacted our ability to provide preventive services in some or possibly all of our schools. In order to continue to provide these services, our community engagement administrator will reach out to those schools where we cannot currently provide in school care, seek their guidance in helping to identify and connect with local community-based organizations in their area and then telephone these local organizations to discuss participation in the research study.

Once an alternate community-based location has been identified and is interested in participating, our HCP will meet with the community organization staff to review COVID-19 safety precautions at the community-based location, clinical protocols, room size and safe distancing requirements. NYUCD HCP will fill out the Caried*Away* COVID-19 community-based location does not meet the requirements listed in the checklist, the NYUCD HCP will notify the Principal Investigator that the site is not an acceptable location for providing safe care.

If the community-based location meets the requirements of the Caried*Away COVID-19* community-based checklist and wishes to participate, the NYUCD HCP will review the Memorandum of Understanding (MOU). As community organizations are identified and sign an MOU we will submit their name and location to the IRB.

All clinical personnel will wear personal protective equipment consistent with CDC, DOH, FDA and NYU Dentistry guidelines.

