7.1 Sample Size Determination

The study is powered to the primary outcomes of caries arrest and caries prevention between twice-yearly simple and complex prevention. We expect to enroll approximately 14,100 students across the initial 60 schools over the duration of the study (N=235 per cluster). The remaining 16 schools will contribute approximately 3760 participants. From our pilot studies of school-based caries prevention, baseline caries prevalence is approximately 40%. Our power estimates assume an equal proportion of success, π , of 20% caries arrest. With a given non-inferiority margin (δ) of 10%, a total sample size per group of 198 (N_{tot} = 396) is required for an alpha of 5% and a power of 80%²⁹. However, as we use a cluster randomized design, this sample size is inflated to account for clustering (intraclass correlation coefficient = .10) by a design effect of 24.4 to a total required sample of 9,662.

For caries prevention, both interim therapeutic restorations and silver diamine fluoride have been shown to be 80% efficacious in individual clinical trials. Power for the repeated measures design was estimated using the method of Diggle et al (2002) for generalized estimating equations ³⁰. For power estimates, we control for the baseline prevalence of untreated decay. We assume a conservative average number of visits per child of 6, with a power of .80 and an alpha of 5%. We further assume a repeated measures correlation of 0.5 and a per-visit attrition rate of 20%. For a given minimally detectable effect size (standardized effect size difference) of .25, an attrition and clustering adjusted sample size of 12,874 is required. Thus, our study is powered for these conservative assumptions for caries prevention. Further, we note that in the presence of the nonlinear link function, ME-GLM is more powerful than GEE, thus our power estimates are conservative and the anticipated sample size is sufficient for analysis.

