8.15 Submission of On-Site Monitoring/Audit and Inspection Reports

Any expectation of violations of protocols will result in an audit of data collection and study assessors. The IRB will receive copies of all study monitoring/audit reports that are submitted quarterly as listed in Table A.

Table A

Data type	Frequency of review	Reviewer
Subject accrual (including compliance with protocol enrollment criteria)	Monthly	PI, Internal QA Reviewer (BEDAC)
	Quarterly	Community Stakeholder Groups
Status of all enrolled subjects, as of date of reporting	Monthly	PI, Internal QA Reviewer (BEDAC)
	Quarterly	Community Stakeholder Groups
Data entry quality control checks on 100% of charts	Weekly	QA Reviewer (BEDAC)
Adherence data regarding study visits and intervention	Weekly	PI, Internal QA Reviewer
	Quarterly	Community Stakeholder Groups
Protocol violations	Weekly	PI, Internal QA Reviewer
	Quarterly	Community Stakeholder Groups
	Annually	PCORI, IRB
SAEs (unexpected and related)	Per occurrence	PI PCORI
SAEs (expected or unrelated)	Per Occurrence	PI, Internal
	Annually	Community Stakeholder Groups PCORI
Unanticipated Problems	Monthly	PI, Internal QA Reviewer
	Per Policy	IRB

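### Intention-to-treat is the only analysis set for the non-inferiority test, with no supportive per-protocol analysis to show whether the conclusion survives missed care

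*Combined protocol and SAP*

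**What the plan says.** Section 2.1 states the primary objective: "To determine if simple prevention is non-inferior to complex prevention for caries arrest and longitudinal caries prevention". Section 7.2 adds: "Our noninferiority margin, δ , is set at 10"%. The margin is stated only in connection with caries arrest.

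On who is analysed, section 7.3 says "For study outcomes, participants will be analyzed using intent to treat" and then "All participants will be analyzed as randomized in the original randomization, regardless of whether or not they received an intervention". It defines no per-protocol or as-treated set, no threshold for adequate exposure and no adherence-adjusted sensitivity analysis. None appears elsewhere.

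The plan foresees missed care. On the COVID-19 closures, section 3.1 says "This has impacted our ability to provide preventive services in some or possibly all of our schools". For the caries-prevention calculation, section 7.1 assumes "a per-visit attrition rate of 20"%, with an average of six visits per child.

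The data needed appear to exist. The review table in section 8.15 lists "Adherence data regarding study visits and intervention" for weekly review, and section 6.6 audits care provision. Against that, sections 5.4 and 8.12.2 mark compliance monitoring and adherence reporting as not applicable.

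**The concern.** In a superiority trial, children who miss their assigned care usually pull the arms together and work against the claim. In a non-inferiority trial the same pull works for the claim. If children in both arms go without care and then have similar outcomes, the observed deficit of simple against complex is smaller than the deficit among children who received care. The test is applied to the smaller figure.

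The trial could then conclude that simple prevention can stand in for complex prevention partly because neither package was fully delivered. With a single analysis set and no prespecified check, a reader of the results could not tell the two explanations apart.

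**Working it through.** **Inputs from the plan.** Section 7.1 assumes success "of 20% caries arrest" in both arms, a margin of 10 points, alpha 5%, power 80%, ICC 0.10 and 235 children per school. Section 3.1 gives 30 schools per arm. I read the margin as a 10-point deficit in arrest for simple against complex. The printed direction of the hypotheses in 7.2 is a separate matter.

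**Reproducing the plan's figure.** n per group = (1.645 + 0.842)² × 2 × 0.20 × 0.80 / 0.10² = 197.8, so 198, as stated. This needs a one-sided 5% test, because one-sided 2.5% gives 252. Design effect = 1 + (235 − 1) × 0.10 = 24.4, and 396 × 24.4 = 9,662. Both match.

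**Effective sample size at planned enrolment.** 30 × 235 / 24.4 = 288.9 per arm.

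**Assumptions not in the documents.** A share m of each arm receives no effective care, and those children have a common arrest rate p0 of 0 or 10%. Among treated children the true rates are 20% (complex) and 10% (simple), a deficit exactly at the margin.

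**Formulas.**
- Observed rate in an arm = (1 − m) × treated rate + m × p0.
- With equal m, the observed deficit d = 10 × (1 − m) points.
- SE = √{[p_c(1 − p_c) + p_s(1 − p_s)] / 288.9}.
- Probability of passing = Φ[(0.10 − d)/SE − 1.645].

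**Worked case, m = 20%, p0 = 0.** Rates are 16% and 8%, so d = 0.08. SE = √[(0.1344 + 0.0736)/288.9] = 0.0268. Then 0.02/0.0268 − 1.645 = −0.899, and Φ = 0.184.

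| Missed care, both arms | Observed deficit | Probability of passing (p0 = 10% to 0) |
|---|---|---|
| 0% | 10 points | 5% |
| 10% | 9 points | about 10% |
| 20% | 8 points | 17–18% |
| 30% | 7 points | 28–32% |
| 40% | 6 points | 42–52% |

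At the required total of 9,662 (198 effective per arm), the m = 20% figure is 14–15%.

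**Larger true deficits.** A 13-point deficit (20% vs 7%) passes with probability of about 1%, 6% and 20–25% at m = 10, 25 and 40%. A 15-point deficit stays below 1% at m = 20%. The risk is concentrated near the margin.

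**Unequal missed care, true 10-point deficit.**
- Complex 30%, simple 10%: with p0 = 0 the observed deficit is 14 − 9 = 5 points and the probability of passing is 60%. With p0 = 10% it is 28%.
- Complex 10%, simple 30%: with p0 = 0 the observed deficit is 18 − 7 = 11 points and the probability is 2.2%, below nominal. With p0 = 10% it is 9.7%.

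**Power of a per-protocol run** (true difference zero, equal exclusion in every school). Cutting 235 to 188 per school gives an effective n of 286.3 and power of 91.1%. Cutting to 141 gives 282.0 and 90.7%. Without exclusions the figures are 288.9 and 91.3%.

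**The case against.** Several points on the other side stand.

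- **Primary set.** The trial is explicitly pragmatic, and intention-to-treat is a defensible primary set. A reader might infer that it is the wrong choice. The documents do not support that. What is missing is a supporting analysis.
- **Direction.** A reader might infer that intention-to-treat always favours non-inferiority here. That needs missed care to be roughly balanced or greater in the complex arm. Section 6.3 gives about 20 minutes for complex and 5 for simple, so balance is not assured, and the reverse pattern can make the test conservative.
- **Size.** It is tempting to say that true deficits of up to 10/(1 − m) points would pass. Such a deficit dilutes to exactly 10 points, and because 7.2 decides by confidence interval it passes only about 5% of the time.
- **Endpoint.** For arrest, 7.2 counts lesions that were treated. Never-treated lesions may leave the denominator, so dilution there comes mainly from missed repeat visits. Caries prevention is more directly exposed, but no margin is stated for it.
- **Attrition.** Examination and care happen at the same visit (6.1.6, 6.2), so a missed visit is also a missing outcome. The 20% per-visit figure is therefore not a measure of dilution. Only children who miss care and are examined later dilute the comparison.
- **Closures.** Section 3.1 says the ability to deliver was affected, not that delivery stopped. Care was extended to community sites and the dental college.
- **Per-protocol sets are selected.** Requiring attendance at every scheduled visit would leave about 0.8⁴ = 41% after four losses of 20% and 0.8⁶ = 26% after six. Giving so selected a subset a veto is hard to defend in a pragmatic trial.

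None of this supplies the missing check. The uncertainty about direction is itself a reason to prespecify one.

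**Conclusion.** The omission is certain: a non-inferiority hypothesis rests on intention-to-treat alone. Its effect is conditional. If missed care is similar in both arms, the chance of passing with a true deficit at the margin rises from 5% to 17–18% at 20% missed care and to 42–52% at 40%. It also rises if complex misses more. If simple misses more, it can fall below 5%.

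These figures rest on the section 7.1 inputs, a one-sided 5% test, and assumed values for missed care and for arrest without care. The documents give no delivered-care rate. They also treat missed care as remaining in the denominator, which the wording of 7.2 leaves in doubt for arrest. They show the order of the risk and do not predict this trial's result. A reader might go further and infer that a non-inferiority finding from this trial would be an artefact of non-delivery. Nothing in the documents supports that.

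**What to change.** Keep intention-to-treat as the primary analysis. In section 7.3:

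1. Add a prespecified supportive per-protocol analysis using the same model, and the 10-point margin where that margin applies, with adjustment for baseline covariates.
2. Define minimum exposure in workable terms: for example, the assigned package at baseline and at a stated minimum share of the visits the study actually offered before the endpoint. A rule tied to offered visits does not penalise children for cancelled visits, but it also leaves closure-driven non-delivery in the set. Item 3 is therefore needed as well.
3. Report delivered care by arm, so that readers can judge the likely direction of any dilution.
4. State that if the per-protocol confidence limit does not exclude a 10-point deficit, the non-inferiority conclusion will be reported as not robust to non-delivery.
5. Reconcile the treated-lesion denominator in 7.2 with the rule in 7.3 that children are kept whether or not they received care.

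The cost is about a paragraph of text and a second run of the same model, on visit and care data that sections 6.6 and 8.15 say are already reviewed. The loss of power is small under the plan's ICC. The downside is that the per-protocol set is smaller and selected after randomisation, so it supports intention-to-treat and does not replace it. It also does not solve the missing-outcome problem.
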